- If no neurological concerns are observed, the study will continue with one additional NCS at week 48 for the first 60 patients. Then for the next enrolled patients, one NCS will be performed at screening and another one at week 48. Additional NCS(s) could be performed between screening and week 48 if any abnormality is detected by the neurological examination or any suggesting symptoms of neuropathy are reported by the patient.
- If NCS show signs of neurological damage, intensive NCS monitoring will continue for all patients at screening and on weeks 4, 12, 24, 36, 48, 60, and 72.

All NCS values will be recorded by the investigator in the eCRF at the corresponding time points.

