### 2.2 Design of the Study

This is a multicenter, multinational, double-blind, randomized (2:1), placebo-controlled Phase III study to investigate the efficacy and safety of 100 mg FAB122 (former TW001) once daily as oral formulation in approximately 300 ALS patients (200 FAB122, 100 Placebo).

Patients will receive double-blind treatment up to a maximum of 72 weeks. The study is planned to continue until the last randomized patient has reached 48 weeks of follow-up (or has reached an intercurrent event) AND the first one third (100) of the randomized patients has reached 72 weeks of follow-up (or has reached an intercurrent event).

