5. The DSMB will assess the results of the NCS for the first enrolled 60 patients (about 40 active and 20 placebo). The NCS will be conducted for the first enrolled 60 patients at screening, and on weeks 4, 12, and 24. Then according to the evaluation by the DSMB, one of the following options will be performed: 1) If no neurological concerns are observed, the study will continue with one additional NCS at week 48 for the first 60 patients. Then for the next enrolled patients, one NCS will be performed at Screening and another one at week 48. Additional NCS(s) could be performed between Screening and week 48 if any abnormality is detected by the neurological examination or any suggesting symptoms of neuropathy are reported by the patient. 2) If NCS show signs of neurological damage, intensive NCS monitoring will continue for all patients at Screening and on weeks 4, 12, 24, 36, 48, 60, and 72.
6. Hematology: hematocrit, hemoglobin, RBC (red blood cell count & parameters), WBC (white blood cell count inclusive differential count), platelet count. Biochemistry: total protein, alkaline phosphatase, AST (aspartate transaminase), ALT (alanine transaminase), GGT (Gamma-glutamyl transpeptidase),

7. Vitamin B6 levels will be monitored and, if necessary, supplementation of vitamin B6 (pyridoxine (100 mg/day)) will be prescribed.
8. Urinalysis: Blood, Glucose, Protein, Specific gravity, Ketone, pH, Nitrite, Leukocytes, Bilirubin, Urobilinogen, Microscopic exam, if abnormal results are noted.
9. Blood sampling for FAB122 PK analysis will be done in ~90 subjects in selected sites. Of those ~30 subjects will participate in a PK profiling sampling schedule and the additional ~60 subjects will participate in a population PK sampling schedule. Sampling schedule for PK profiling: pre-dose and 15 min, 30 min, 1, 1.5, 2, 4 hrs., and 6hrs. after the FAB122 morning dose. The pre-dose sample may be collected within 30 minutes prior to dosing, the samples taken 15 and, 30 min post dosing samples should be taken within ±2 minutes of the scheduled time, the 1 hr. post dosing sample within ±5 minutes, the 2-hour sample within ±10 minutes and the 4 hr. and 6hr. sample within ±20 minutes of the scheduled time. The time of sampling will be accurately recorded. Sampling schedule for population PK: (1) pre-dose (within 1 hour prior to dosing), (2) within 5- and 30-minutes post dosing, (3) 1 hour and (4) 1.5 hour after the second PK sample was taken.

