# **5 STATISTICAL ANALYSIS**

## **5.1 General considerations**

Raw data (in listings) will be presented in the same precision as received. Appropriate rounding will be performed for the summary statistics: arithmetic mean, median, SD (standard deviation) and confidence limits will be presented with one more decimal than the original data; minimum and maximum values will be presented with the same precision as the original data. In frequency tables, percentages will be presented with 1 decimal. P-values will be presented with 3 decimals, and those smaller than 0.001 will be replaced by <0.001.

Descriptive statistics presented in general summary tables will be the number of non-missing observations (n), mean, SD, minimum, median and maximum for quantitative data. For categorical data, frequency counts and percentages will be determined. The denominator when calculating percentages will be the number of patients in the applicable analysis population. Descriptive statistics will be displayed for all visits that a measurement is collected on, even if the endpoint is only referring to limited visits for the analysis.

Baseline is defined as the last value measured prior to first study treatment administration, unless otherwise specified. In case this value is missing for a specific patient, but an earlier measurement (e.g. screening) is present, this value will be used as baseline instead. Unscheduled measurements are excluded as baseline value.

If available in the database, data for screening failures will not be presented in summary tables, except for disposition and end-of-study displays. Data for screening failures will be listed as available.

For patients that are unable to attend the clinic on a study visit due to ALS progression, at least ALSFRS score, AEs and concomitant medication data are collected. These data may be collected by telephone and are considered of the same quality as performed during live visits.

If a patient is not able to attend the site for two consecutive visits, then IMP will be discontinued at the 2nd missed visit, but participation in the trial and data collection can continue via telephonic visits to collect ALSFRS-R, AE and concomitant medication. It is assumed that data collected via telephone visits is of same quality as the data collected via site visits.

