### **5.3 Mapping of unscheduled or early termination visits**

When visit assessments are missing, repeat assessments performed within the agreed time window of +/- 7 days will be mapped to the appropriate visit in the database by the DM vendor. Repeat assessments performed outside of these agreed time windows are collected in the database using an unscheduled visit. For these unscheduled assessments following a missing protocol visit, mapping will be done to the (closest) protocol visit at which the applicable assessment should have been performed before the date of unscheduled visit.

In case of a repeated or additional assessments for non-missing assessments, mapping will only be done for replacement if this is clearly agreed (at patient and visit level) with the client and specified by DM vendor (e.g. because it replaces an erroneous measure collected at the actual visit), and as such will be used in statistical data presentations. These agreements will be documented during the BDRM.

For patients that withdraw early from the trial, an early termination visit is scheduled 7-14 days after withdrawal, for which the same procedures as for visit 8 will be performed. The data of this early withdrawal will be mapped to the most appropriate scheduled post-baseline visit as applicable per assessment, to be agreed together with the DM vendor and the client on occurrence. The documentation of these agreements is to be finalized during the BDRM. For early termination visits in general mapping will be done to the closest protocol visit at which the applicable assessment should be performed after the date of early termination.

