## **5.7 Safety and tolerability evaluation**

All safety presentations will be created using the SAF population.

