### **5.7.7 Nerve conduction study (NCS)**

NCS consists of the following assessments: Hand Temperature (°C), Foot Temperature (°C), SRAR, SNAP (µV) and SCV (m/s). The latter two have been determined for locations Median Nerve, Ulnar Nerve, Radial Nerve, Sural Nerve. Descriptive statistics will be presented for all assessments, irrespective of being performed per NCS protocol or quality assessment result. The following descriptive displays will be presented:

- Descriptive statistics per visit and treatment arm, including change from baseline.
- Mean +/- SD plots versus time
- Shift from baseline categories (presenting frequencies and percentages per visit and treatment arm)
- Percentage drop >50% from baseline (presenting frequencies and percentages per visit and treatment arm)
- Normal/abnormal classification results (presenting frequencies and percentages per visit and treatment arm)

Information on high/low/normal categorization is presented in section 9.1.

In case of multiple measurements for a specific visit, repeats have occurred because of a measurement being not quality approved. In those instances, the last repeated value will be used for the descriptive statistics. All collected values will be listed.

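### The SAP divides nerve conduction counts at weeks 4, 12 and 24 by the whole safety arm, although testing then may be limited to the first 60 patients, so printed rates are too low by a factor of about 1 to 5

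*SAP*

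**What the plan says.** Three rules in the SAP combine.

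- Section 5.7.7 asks for three categorical NCS displays: shift from baseline, "Percentage drop >50% from baseline (presenting frequencies and percentages per visit and treatment arm", and "Normal/abnormal classification results (presenting frequencies and percentages per visit and treatment arm". It gives no denominator of its own.
- Section 5.7 fixes the population: "All safety presentations will be created using the SAF population".
- Section 5.1 fixes the divisor: "The denominator when calculating percentages will be the number of patients in the applicable analysis population".

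The safety population is everyone randomized and dosed, and section 2.2 plans the study "in approximately 300 ALS patients (200 FAB122, 100 Placebo".

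The testing schedule is narrower. SAP section 2.5, footnote 5, states: "The NCS will be conducted for the first enrolled 60 patients at screening, and on weeks 4, 12, and 24". Protocol Table 1 (footnote 5) and Protocol 8.2.5 say the same and put the split at about 40 active and 20 placebo. What follows depends on the DSMB. If it sees no neurological concern, later patients are tested at screening and week 48, with extra tests when examination or symptoms call for them (the no-concern option). If it sees damage, all patients are tested at weeks 4, 12, 24 and onward (the damage option). Neither document says which option was taken.

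The protocol is not uniform on the limit of 60. The NCS rationale in section 2.1 and the lists for Visits 2 to 4 in section 6.3 give NCS at weeks 4, 12 and 24 without it.

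**The concern.** A percentage in a safety table is read as a rate among patients who were examined. Followed literally, the SAP counts patients who had no NCS scheduled at a visit as if they had been tested and found normal.

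NCS is in the trial because animal studies showed neurotoxicity at low safety margins (Protocol 2.2), and it is meant to find subclinical sensory damage early (Protocol 8.2.5). The week 4 to 24 data are the early on-treatment evidence on that question. Two things are at stake in the study report: the absolute abnormality rate and risk difference at those visits, and the pattern over time, since the share of the arm tested can differ from visit to visit.

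**Working it through.** **Arm sizes.** SAP 2.4 gives a difference of 3.0, SD 7.5, 2:1 allocation, 90% power and 5% two-sided alpha. Placebo n = (1 + 1/2) × (1.960 + 1.282)² × 7.5² / 3.0² = 98.5, so 99, and 297 in total. With 200 and 100 the power is 0.904. The planned 300 is reproduced. The documents state no NCS abnormality rate, so there is no planned NCS figure to reproduce.

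**Formula.** Dilution factor at a visit = planned safety arm ÷ number tested at that visit, before attrition. Tested patients are assumed to split 2:1, so the factor is the same in both arms.

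**First 60 only, no-concern option, no triggered tests.** 200/40 = 100/20 = 5. Even if every tested patient were abnormal, the table could print no more than 40/200 = 20/100 = 20.0%. If 5%, 10% or 20% of the other 240 patients had a triggered test counted at the visit (assumed), 72, 84 or 108 would be tested and the factor would be 4.2, 3.6 or 2.8.

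**Other readings.** Assume uniform accrual of 300 over the planned 10 months (30 a month) and a DSMB decision as soon as patient 60 reaches week 24. Twenty-four weeks is 5.52 months, so the decision falls at 60/30 + 5.52 = 7.52 months. By then the number of patients already past each visit is:

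- week 4: 30 × (7.52 − 0.92) = 198
- week 12: 30 × (7.52 − 2.76) = 143
- week 24: 30 × (7.52 − 5.52) = 60

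| Reading | Tested at weeks 4 / 12 / 24 | Factor |
|---|---|---|
| First 60 only, no-concern option | 60 / 60 / 60 | 5.0 / 5.0 / 5.0 |
| First 60, then damage option | 162 / 217 / 300 | 1.9 / 1.4 / 1.0 |
| Everyone until the decision (section 2.1 and Visit 2 to 4 lists), then no-concern option | 198 / 143 / 60 | 1.5 / 2.1 / 5.0 |

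In the second row the number tested is 300 minus the patients from 61 onward who had already passed the visit: 300 − (198 − 60) = 162, and likewise for the others. A DSMB lag of two months would raise that row to 2.9 / 1.9 / 1.25.

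**Effect on a difference (assumed counts, first row).** With a >50% drop in 4 of 40 active and 1 of 20 placebo patients, the rates are 10.0% and 5.0%, 5.0 points apart. The SAP rule prints 4/200 = 2.0% and 1/100 = 1.0%, 1.0 point apart. The ratio of 2 is kept.

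**Effect on a trend (assumed flat 10% among tested active patients).**

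- First row: 2.0% at weeks 4, 12 and 24. At week 48, when 8.2.5 schedules everyone, it prints 7.0% to 9.0% if 70% to 90% are tested (assumed).
- Second row: 10% × 162/300, 217/300 and 300/300 = 5.4%, 7.2% and 10.0%, an apparent rise.
- Third row: 10% × 198/300, 143/300 and 60/300 = 6.6%, 4.8% and 2.0%, an apparent fall.

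**The case against.** The strongest reply is that the damage is limited. Counts stand beside the percentages, the quantitative NCS tables print n per visit, and all NCS values are listed. Significant NCS abnormalities are adverse events of special interest (Protocol 9.1.4) with their own table and listing. The DSMB works from a separate SAP. This SAP attaches no test or decision rule to NCS. All of that stands, and it keeps the point to descriptive tables.

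It might also be said that percentages per visit and arm already imply a per-visit divisor. That phrase describes layout and does not clearly override section 5.1. Section 5.2 shows the convention is deliberate: for efficacy it prints the number without missing data and still divides by the population.

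Two stronger readings are tempting, and the documents support neither.

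- *The rates are five-fold too low, without condition.* This needs the first-60 schedule to override section 2.1 and the visit lists, the no-concern option, and few triggered tests. The visit lists mark NCS as conditional only from week 36 on, and the DSMB's choice is not stated.
- *Symptom-triggered tests will be pooled into weeks 4 to 24.* Protocol 8.2.5 does allow them: "Additional NCS(s) could be performed between screening and week 48 if any abnormality is detected by the neurological examination". SAP 5.7.7 has no exclusion like those for unscheduled laboratory, vital sign and ECG data, and it presents assessments whether or not they followed the NCS protocol. But under section 5.3, "mapping will be done to the (closest) protocol visit at which the applicable assessment should have been performed before the date of unscheduled visit" applies only after a missing protocol visit. On the first-60 schedule, patients from 61 onward have no missing NCS at weeks 4 to 24 under the no-concern option, so nothing maps. On the unrestricted visit lists mapping is possible, but NCS is then scheduled for everyone and the schedule itself causes no dilution. An extra test beside a non-missing one replaces it only by documented agreement for that patient and visit. No number of triggered tests is given from which to size an effect.

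**Conclusion.** The denominator fault holds. Applying sections 5.1, 5.7 and 5.7.7 as written divides week 4, 12 and 24 NCS counts by patients who may never have been scheduled for the test. Absolute rates and risk differences at those visits are then too low by a factor of about 1 to 5. The upper end needs the first-60 schedule, the no-concern option and few triggered tests. The lower end is the damage option by week 24. The intermediate values rest on planned arm sizes, a 2:1 split among those tested, uniform 10-month accrual and no DSMB lag, all before attrition.

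Where the factor differs between visits, a flat rate can print as a rise or a fall, and a reader who does not know which option applied cannot correct for it from the percentages alone. Between-arm ratios, counts, listings, special-interest event tables, DSMB review and all efficacy analyses are unaffected. The point is worth correcting before database lock because the rule is explicit, the resulting rates are wrong, and the repair is small.

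**What to change.** Add one sentence to SAP 5.7.7: for the shift and >50% drop tables, the denominator is the number of safety-population patients in the arm with a baseline and a value at that visit; for the normal/abnormal table, it is the number with a non-missing value at that visit; this n is printed in each table. The rule is right under every reading of the schedule and either DSMB option, and needs no protocol change and no additional test.

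The cost is SAP wording and table programming. There are two downsides. NCS denominators will differ from those of the other safety tables, which a footnote can explain. And early rates may visibly rest on about 40 and 20 patients: for the assumed counts, 4/40 = 10.0% has an exact 95% interval of 2.8% to 23.7%, and 1/20 = 5.0% has 0.1% to 24.9%. That width reflects the information actually collected.

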### **5.7.8 Other examinations**

Any other data collected will be presented in listings.

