## 2.2. Risk-Benefit Assessment

ALS is a devastating neurological disease for which there is no cure and an urgent unmet need persists for effective therapies. The main aims in the care of these patients are to minimize morbidity and maximize quality of life. Riluzole (Europe and USA) and iv edaravone (USA) are the only current approved drugs for ALS.

In general, long-term treatment with intravenously administered edaravone showed clinical benefit and an acceptable safety profile in ALS patients. As well, single- and multiple dose of FAB122 was safe and well tolerated in ALS patients and healthy volunteers.

The animal toxicology studies revealed neurologic adverse findings (e.g. abnormal gait, decreased activity, prostration, reduced function of the hind limbs) with prolonged exposure to edaravone at relatively low safety margins compared to the anticipated human exposure levels. Analysis of the non-clinical data indicated that the neurotoxic effects seen after edaravone administration resulted from demyelination (primary effect) followed by axonal degeneration (secondary effect). Therefore, special monitoring of potential neurotoxicity will be performed by NCS during the conduct of the current study (For more details, see FAB122 IB).

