### **8.2.1. Physical and neurological examination**

Physical examinations will be performed by qualified personnel according to the Schedule of Events. Symptom directed physical exams will be performed as applicable. Physical examination includes the following assessments: general appearance, head, eyes, ears/nose/throat, neck, lymph nodes, skin, lungs, heart, abdomen, musculoskeletal, and neurologic evaluations. Breast, rectal, and genitourinary/pelvic exams should be performed when clinically indicated. Weight (kilograms) will be measured as part of all physical examinations. Height (centimeters) will be measured only at the screening visit. The BMI will be calculated.

Neurological examination will be performed by qualified personnel according to the Schedule of Events to assess possible peripheral nerve dysfunction (= sensory or motor symptoms), diminished or absent reflexes (compared with baseline examination), sensory abnormalities (e.g. numbness or tingling) or weakness. In case a subject experiences clinical signs or symptoms at home, subjects will be asked to contact the clinic.

All abnormal findings will be documented in the database.

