### 9.1. Definitions

#### 9.1.1. Adverse Event

An AE is any unfavorable and unintended sign (including an abnormal laboratory finding), symptom, or disease temporally associated with the use of a medicinal (investigational) product, whether or not related to the medicinal (investigational) product. An AE is any symptom, sign, illness, or experience that develops or worsens in severity during the course of the study. Adverse events reported after consent but before the first dose of study drug are still to be documented by the investigator but will be considered non-treatment-emergent AEs.

Intercurrent illnesses or injuries should be regarded as AEs. Abnormal results of laboratory tests or diagnostic procedures are considered to be AEs if the abnormality:

- Is associated with clinical signs or symptoms
- Is considered by the investigator to be of clinical significance
- Results in study withdrawal
- Fulfils any of the criteria for a SAE, as described in this section
- Requires intervention or further evaluation to determine the etiology of the abnormality and/or assess the risk to the subject
- Requires treatment

Changes in ALS symptoms will not be documented as AEs unless they are extraordinary and/or unexpected. In the same way planned hospitalizations for procedures which are related to the patient's disease, and are expected within the evolution of the ALS symptoms (i.e. PEG procedure; Mechanical ventilation set up) will not be considered as SAEs unless they are extraordinary and/or unexpected and/or of they meet other seriousness criteria.

---

A treatment-emergent adverse event (TEAE) is defined as an adverse event observed after the first dose of study drug. If a subject experiences an event both prior to and after starting study drug administration, the event will be considered a TEAE (of the treatment) only if it has worsened in severity (i.e., it is reported with a new start date) after study drug administration of the specific treatment, and prior to the start of another treatment, if any.

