## 2.5 Study assessments

	Screening	Baseline	Treatment period															
			V1 D1 W0	V2 D28 W4 ±3D	T1 D56 W8 ±4D	V3 D84 W12 ±3D	T2 D112 W16 ±4D	T3 D140 W20 ±4D	V4 D168 W24 ±7D	T4 D196 W28 ±7D	T5 D224 W32 ±7D	V5 D252 W36 ±7D	T6 D280 W40 ±7D	T7 D308 W44 ±7D	V6/EoT D336 W48 ±7D	V7 D420 W60 ±7D	V8  D504 W72 OR EoT 	
Administrative procedures																		
ICF	X																	
ICF for PK	X																	
In/exclusion criteria	X	X 																
Medical history	X																	
Prior/Concomitant medication			X-----X															
Randomization	X																	
Dispensing study medication/Compliance check	X*			X					X			X			X	X		
Clinical Procedures																		
Physical examination	X	X							X						X	X		
Weight	X	X							X						X	X		
Height	X																	
Vital Signs	X	X	X	X					X			X			X	X	X	
12-lead ECG	X	X							X						X	X	X	
Neurological examination 	X	X	X	X					X			X			X	X	X	
NCS 	X*		X	X					X									
(S)AE monitoring		X-----X																
Laboratory procedures																		

	Screening	Baseline	Treatment period															
			V1 D1 W0	V2 D28 W4 ±3D	T1 D56 W8 ±4D	V3 D84 W12 ±3D	T2 D112 W16 ±4D	T3 D140 W20 ±4D	V4 D168 W24 ±7D	T4 D196 W28 ±7D	T5 D224 W32 ±7D	V5 D252 W36 ±7D	T6 D280 W40 ±7D	T7 D308 W44 ±7D	V6/EoT D336 W48 ±7D	V7 D420 W60 ±7D	V8  D504 W72 OR EoT 	
Chemistry/Haematology 	X	X 	X		X				X			X			X	X	X	
Vitamin B6 monitoring 	X	X	X	X					X			X			X	X	X	
Urinalysis 	X	X	X	X					X			X			X	X	X	
β-hCG 	X																	
Urine Pregnancy Test 	X	X	X	X					X			X			X	X	X	
HIV/Hepatitis B,C	X																	
ALS evaluation procedures																		
ALSFRS-R	X	X	X	X	X	X	X	X	X	X	X	X	X	X	X	X	X	
SVC	X	X		X					X			X			X	X	X	
HHD		X		X					X			X			X	X	X	
ALSAQ-40	X								X							X		
ECAS		X							X						X			
EQ-5D-5L	X			X					X			X			X	X	X	
VAS		X		X					X			X			X	X	X	
Cost questionnaire	X			X					X			X			X	X	X	
King's staging system and MiToS	X			X					X			X			X	X	X	
PK																		
Blood sampling for FAB122 	X 	X 														X 	X 	
Blood sampling for riluzole 	X	X																
ALS biomarkers																		
Blood sampling for biomarkers 		X	X		X				X			X			X	X	X	
Urine collection for biomarkers 		X	X		X				X			X			X	X	X	

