## 10.4 Listings

Following ICH E3 guidelines, all listings mentioned here will be presented in Section 16.2 of the CSR, and listings will be prepared in the order and with section number as stated.

Individual listings will be prepared of all the data collected in the database, following SDTM data format. No combining of data other than mentioned in this paragraph will be performed. The key variables in the listings (except a few displaying screening data) will be patient number and treatment. If applicable, visit number will be listed additionally. Furthermore, a listing containing study visit dates will be presented.

Listing number	Contents of listing
16.2.1 Discontinued patients	
16.2.1.1	Inclusion/exclusion criteria – description
16.2.1.2	Inclusion/exclusion criteria – deviations
16.2.1.3	Patient disposition
16.2.2 Protocol deviations	
16.2.2	Protocol deviations
16.2.3 Demographic and baseline data	
16.2.3.1	Demographics
16.2.3.2	Randomization
16.2.3.3	Substance use
16.2.3.4	Medical history
16.2.3.5	ALS history
16.2.3.6	Pregnancy test
16.2.4 Compliance and/or treatment data	
16.2.4.1	Treatment exposure
16.2.4.2	Drug accountability and compliance
16.2.4.3	Study visits
16.2.5 Individual efficacy response data	
16.2.5.1	ALSFRS-R
16.2.5.2	CAFS

16.2.5.3	King's staging system
16.2.5.4	MiToS
16.2.5.5	SVC
16.2.5.6	HDD
16.2.5.7	QoL
16.2.5.8	Cognition (ECAS)
16.2.5.9	Biomarkers
16.2.5.10	Cost-utility
16.2.5.11	Survival
16.2.6 Adverse event listings	
16.2.6.1	Adverse events
16.2.6.2	AEs leading to discontinuation from the study
16.2.6.3	Vital signs
16.2.6.4	ECG
16.2.6.5	Physical Examination
16.2.6.6	Neurological examination
16.2.6.7	Nerve conduction study
16.2.6.8	Prior and concomitant medication
16.2.7 Listing of individual laboratory measurements by patient	
16.2.7.1	Laboratory safety data – haematology
16.2.7.2	Laboratory safety data – clinical chemistry
16.2.7.3	Laboratory safety data – urinalysis
16.2.7.4	Laboratory safety data – coagulation
16.2.7.5	Laboratory safety data – serology
16.2.7.6	Laboratory safety data – Vitamin B6
16.2.7.7	General comments

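### The neurological examination, scheduled at every clinic visit to look for peripheral nerve dysfunction, gets a patient listing in the SAP but no table by arm

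*SAP*

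**What the plan says.** Protocol 8.2.1, under Safety Parameters, states the purpose: "Neurological examination will be performed by qualified personnel according to the Schedule of Events to assess possible peripheral nerve dysfunction". The examination covers symptoms, reflexes judged against baseline, sensory abnormality and weakness. The same section adds: "All abnormal findings will be documented in the database". Protocol 6.1 to 6.3 and SAP 2.5 schedule it at screening, baseline and weeks 4, 12, 24, 36 and 48, and at weeks 60 and 72 for those followed that long. It is not restricted to a subset.

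The reason for the neurological monitoring is in Protocol 2.2, which reports neurologic findings in animals at low exposure margins and continues: "Therefore, special monitoring of potential neurotoxicity will be performed by NCS during the conduct of the current study".

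On analysis, Protocol 11.3.6 says in general that safety variables are tabulated in the Safety Population and summarised by treatment and time. Section 11.3.6.1 asks for physical-examination abnormalities to be both listed and tabulated by arm. In the SAP, 5.7.6 deals with the physical examination, 5.7.7 with NCS, and 5.7.8 covers the rest: "Any other data collected will be presented in listings". That sentence does not name the neurological examination. The direct evidence is in the output lists. SAP 10.4 has listing 16.2.6.6, "Neurological examination", while SAP 10.3 names tables for the physical examination (14.3.4.10) and NCS (14.3.4.11.x) but none for this examination.

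**The concern.** In ALS, weakness and reflex change are expected in both arms. A patient listing cannot show whether FAB122 adds to that background, because each finding can be put down to the disease. Only rates by randomised arm can show an excess. The examination is the clinical check scheduled most widely for the toxicity that the animal data point to, and as planned it ends in individual listings. Laboratory data, vital signs, ECG and NCS are all summarised over time by arm or visit. If the report is later asked whether clinical signs of nerve dysfunction were more frequent on active treatment, the planned output has no direct answer.

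**Working it through.** There is no stated figure to reproduce. The check traces the examination through both documents, asks what the neighbouring outputs catch, and sizes what is left.

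**1. Planned output for each assessment**

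| Assessment | Scheduled in | Protocol analysis text | SAP text | SAP 10.3 table |
|---|---|---|---|---|
| Neurological examination | All patients, every clinic visit | General statement in 11.3.6 only | None specific; catch-all in 5.7.8 | None (listing 16.2.6.6) |
| Physical examination | Screening, baseline, weeks 24, 48, 72 | 11.3.6.1: listing and by-arm tabulation | 5.7.6: listing only | 14.3.4.10 |
| NCS | All patients; timing depends on the DSMB decision | None specific | 5.7.7: by visit and arm | 14.3.4.11.x |

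The physical-examination row is a separate inconsistency: SAP 5.7.6 omits the tabulation that the protocol asks for, yet SAP 10.3 still names a table. SAP section 6, on changes from the protocol, does not mention it.

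**2. What the other outputs catch**

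- *Adverse events of special interest.* Protocol 9.1.4 includes significant NCS abnormalities and any adverse event suggesting neuropathy, with numbness as its example. SAP 5.7.1 tabulates these. But Protocol 9.1.1 says: "Changes in ALS symptoms will not be documented as AEs unless they are extraordinary and/or unexpected". Sensory complaints therefore have a tabulated route, while weakness or reflex loss attributed to ALS normally does not.
- *NCS.* If the DSMB sees no neurological concern, Protocol 8.2.5 says: "Then for the next enrolled patients, one NCS will be performed at screening and another one at week 48". Between those two points, extra NCS depends on an abnormal neurological examination or reported symptoms, so the examination is the scheduled check in that interval.
- *Physical examination.* It includes neurologic evaluations (8.2.1), but at fewer visits, and its tabulation is itself unsettled.
- *DSMB.* It reviews clinical signs once about 60 patients have 24 weeks of treatment (Protocol 2.1), under a separate SAP.

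**3. Volume of data**

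Inputs: 300 patients; five post-baseline clinic visits to week 48; two more for the first 100; no dropout assumed.

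- Neurological examinations: 300 × 5 + 100 × 2 = 1,700, listed only.
- Scheduled NCS under the no-concern option of 8.2.5: 60 × 4 + 240 × 1 = 480, all summarised by arm. The week 4, 12 and 24 visit lists in Protocol 6.3 show NCS without a subset restriction, so the actual number could be higher.

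**4. Precision a by-arm table would give**

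The documents give no rates of neurological signs, so the rates below are assumptions. The 95% half-width for the risk difference is 1.96 × √[p₀(1 − p₀)/n₀ + p₁(1 − p₁)/n₁].

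| Placebo p₀ | FAB122 p₁ | Half-width, 100 vs 200 examined |
|---|---|---|
| 5% | 10% | 6.0 points |
| 5% | 15% | 6.5 points |
| 10% | 20% | 8.1 points |
| 20% | 35% | 10.3 points |

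If only 70 and 140 patients are examined (an assumed 70% attendance), each half-width grows by √(100/70) = 1.195, giving about 7 to 12 points.

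**The case against.** The strongest reply is that neurotoxicity is already covered by arm. A reader might infer from the 60-patient DSMB review that the final conclusion would rest on NCS in a subset of about 40 active and 20 placebo patients. The documents do not support that. The 60 are the DSMB look; under either DSMB option all patients are to have NCS at least at screening and week 48, and SAP 5.7.7 summarises it by visit and arm, including shifts from baseline and normal/abnormal frequencies against the limits in SAP 9.1. A power comparison between 200:100 and 40:20 would therefore describe an analysis nobody plans. This part of the reply stands.

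It is also true that Protocol 8.2.5 expects a mainly sensory neuropathy and that sensory adverse events reach the special-interest table. That route depends on investigator reporting and does not carry ALS-like signs, so it narrows the gap without closing it.

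Three further points stand as limits. The protocol's commitment is general: neither its safety endpoints nor the opening of 11.3.6 names this examination, so no specifically promised table has been dropped. The SAP's safety outputs are descriptive throughout, so the absence of a formal test is not peculiar to this variable. And the CRF is not available here, so whether individual signs are coded comparably with baseline cannot be confirmed.

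**Conclusion.** The gap holds and is moderate. A protocol safety parameter aimed at peripheral nerve dysfunction has a listing and no summary by arm, and the outputs around it cover it only in part. What is lost is the by-arm rate of new clinical signs, above all reflex loss and weakness attributed to ALS. Under the assumed rates, a table could place the difference within roughly 6 to 10 points at full attendance, or 7 to 12 at 70% attendance. Those widths are illustrative.

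The point does not mean that neurotoxicity goes unassessed between arms, and Protocol 2.2 speaks of potential neurotoxicity from animal findings, not of an established human risk. The conclusion rests on the section texts and output lists. The 1,700 examinations are a ceiling: patients followed by telephone give only ALSFRS-R, adverse events and concomitant medication (Protocol section 6; SAP 5.1).

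**What to change.** Add one descriptive table to SAP section 14.3 outputs, with a short subsection in 5.7 to define it. By arm, at each visit and at any post-baseline visit, give the number of patients with a new or worsened abnormality versus baseline: sensory abnormality, reduced or absent reflex, and weakness, at whatever detail the CRF records. Use patients actually examined as the denominator, and show the risk difference with its 95% CI, without a formal test.

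Reconcile SAP 5.7.6 with Protocol 11.3.6.1 and table 14.3.4.10, so that it is clear whether physical-examination abnormalities are tabulated by arm; record any departure in SAP section 6.

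Optionally, add to the planned NCS tables a combined flag for the neuropathy criterion in Protocol 8.2.5 (low sural SNAP or low SRAR), restricted to cases not present at baseline.

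The cost is one table, a check of how the CRF codes the findings, and a wording correction. No extra assessments are needed, and neither the primary analysis nor the testing hierarchy changes.
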